## 6.2 Secondary Outcome Measure

#### **Sheehan Disability Scale (SDS)**

The SDS is a clinician-rated assessment of functional impairment [73]. The items indicate degree of impairment in the domains of work/school, social life, and home life, with response options based on an eleven-point scale (0=not at all to 10=extremely), and five verbal tags (not at all, mildly, moderately, markedly, extremely). For participants who are not able to work for reasons related to PTSD, the functional impairment item will be scored as a 10. The SDS takes 1 to 2 minutes to complete [73, 74].

#### **6.3 Safety Measures**

## Columbia Suicide Severity Rating Scale (C-SSRS)

The C-SSRS is a clinician-administered measure of suicidal behavior devised to detect potential suicidal thoughts or behaviors during a clinical trial [75]. It consists of a Lifetime version and a Since Last Visit version that assess suicidal ideation, ideation intensity, and behavior. The C-SSRS consists of a series of questions, and can be administered during a face-to-face interview or over the telephone. The Lifetime version will only be administered at the initial Screening visit. All subsequent administrations will utilize the Since Last Visit version. Participants who are discontinuing medications to participate in the study will complete the C-SSRS before and after medication washout. The C-SSRS Intensity scale for Lifetime obtained a Cronbach's alpha of 0.93 and 0.94 for the Since Last Visit form, and Last Visit C-SSRS severity scores were positively correlated with the BDI "suicide thoughts" item [76].

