**Table 1: Study Design Overview** 

	Screening Period			
	From Consent to Enrollment (Visit 0): ~4 weeks (+  Study Visit Visit Duration/		Brief Description of Events	
Stu	ry visit	Visit Timing/ (Scheduling Window)	-	
Screening	Screening	Multiple visits over 3 weeks (-2 weeks/+1 week) 7 to 28 days total	At initial visit, obtain Informed Consent and assess all screening measures (including LEC-5, PCL-5, Lifetime C-SSRS, AUDIT, DUDIT), medical history, and pre-study medications. Contact outside providers and order medical records, physical exam, labs (including pregnancy and drug tests), ECG, and 1-minute rhythm strip. Once all results and records are obtained, review along with notes from all screening visits and measures. If eligible, send results of LEC-5 & CIPD-SR to IR. Screening may take place over 3 weeks at multiple visits.	
	Independent Rater Screening	1 hour/ 2 days after initial eligibility established in Screening (+7 days)  2 to 9 days after initial eligibility established	After PCL-5, and initial eligibility are reviewed, an IR will conduct the Since Last Visit C-SSRS, CIPD, DDIS, and MINI via tele-assessment. Results will be confirmed by clinical observation during the Preparatory Period, but the CIPD-SR, DDIS, and MINI will not be repeated.	
Enrollment	Enrollment (Visit 0)  1.5 hours/ 2 days after (+12 days) Independent Rater Screening  2 to 14 days after IR Screening		Prior to enrolling: review all screening measures, medical history, discussion with outside providers and sponsor, and any clarification phone calls with participant. Visit is 1.5 hours to review eligibility and medical tapering plan. If enrolled, begin taper, (5 half-lives plus 1 week for stabilization). Adverse Event (AE) collection begins.	

	Preparatory Period with Enrollment Confirmation From Preparatory Session 1 (Visit 1) to Preparatory Session 3 (Visit 4): ~6 weeks (+5/-4 weeks)				
Study Visit #	Visit/	on 1 (Visit 1) to Preparatory  Visit Duration/  Visit Timing/	Brief Description of Events		
V ISIL 7	r	(Scheduling Window)			
	Preparatory Session 1 (Visit 1)	1.5 hours/ Within 1 week (-7/+5 days) after Enrollment (V0)  0 to 12 days after Enrollment (V0)	90-minute Preparatory Session. Target visit timing on tapering needs. If needed, schedule calls between V1 and V2 if indicated for tapering, safety, or further questions about medical history.		

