Preparatory Period	Preparatory Session 2 (Visit 2)	1.5 hours/ At least 2 days after Preparatory Session 1 (V1); within 3 weeks of Preparatory Session 1 (V1)  2 to 21 days after Preparatory Session 1 (V1)	90-minute Preparatory Session/ongoing assessment.  If tapering is complete or not needed, check eligibility and schedule V3 and V4. If tapering is ongoing, schedule post taper call for ongoing assessment.		
Prep	Phone Call End Taper	1 hour/ Within 1 week of planned taper end & stabilization off medications; before Baseline CAPS T1 (V3); within 8 weeks of V0  0 to 56 days after	If needed, confirm medication taper and stabilization is complete and participant is eligible for Baseline CAPS-5. Schedule V3 and V4.		
		Enrollment (V0); within 7 days of the end of tapering and stabilization; prior to baseline CAPS T1 (V3)			
Baseline & Enrollment Confirmation	Baseline CAPS-5 T1 (Visit 3)	1.5 hours/ Post Preparatory Session 2 (V2) & confirmation of Medication Taper and stabilization; before V4	CAPS-5, SDS, and DSP-I completed by an IR via tele-assessment after taper is complete. CAPS-5 scores sent ASAP to the therapy team/Principal Investigator.		
Basel		At least 7 days after Preparatory Session 2 (V2)			

Preparatory Session 3 & Enrollment Confirmation (Visit 4)	3 hours: (90 minutes of measures, 90-minute therapy) Within 6 days of Baseline CAPS T1 (V3); within 4 days prior to Experimental Session 1 (V5) but not on the same day  3 to 6 days after Baseline CAPS T1 (V3); 1 to 4 days before Experimental Session 1 (V5). Both Baseline CAPS T1 (V3) and Preparatory Session 3 and Enrollment Confirmation (V4) must take place within 7 days prior to Experimental Session 1 (V5).	Prior to visit, ensure CAPS-5 confirms PTSD diagnosis and Total Severity Score of ≥35 and confirm enrollment by reassessing specified eligibility criteria. Complete Baseline self-report measures. Complete 3-hour Preparatory Session (~90-minute measures, 90-minute therapy) and schedule V5. If enrollment is not confirmed do not perform visit, complete termination.
---	---	--

Stu Visi	ly Visit/ t #	Visit Duration/ Visit Timing/ (Scheduling Window)	Brief Description of Events	

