## 4.3.3 Pre-Dosing Early Terminations

'Pre-Dosing Early Terminations' are defined as participants who were deemed eligible and enrolled in the study at Visit 0, but are deemed ineligible prior to the first Experimental Session and do not have enrollment confirmed at Visit 4. These participants may fail to meet all Inclusion Criteria and may meet one or more Exclusion Criteria or withdraw consent prior to Enrollment Confirmation or the site may withdraw the participant for reasons described in Section 5.3.4 Early Termination from the Study). Participants who fail Enrollment Confirmation may not be re-

enrolled into this study at a later date. All enrolled participants, even those failing Enrollment Confirmation, will be maintained in the EDC system. Pre-Dosing Early Terminations are not considered evaluable.

Pre-Dosing Early Terminations may be identified through review of medical history, assessments, measures, laboratory results, or conversations with the participant. At any time during the Preparatory Period, if a potential participant is deemed to be ineligible, classify as a Pre-Dosing Early Termination, notify the potential participant that they are not eligible for the study, and do not schedule additional assessments. Do not perform the next visit. Pre-Dosing Early Terminations will be provided an Exit Plan as described in Section 7.4.4 Exit Plan.

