**Table 7: Time and Events – Study Measures** 

		Screening		Enrollment Confirmation			Treatment 1				Treatment 2			Follow-up & Study Termination	
	Visit #	Site A	IR Screening	IR V3	V4	V5	V6&7	IR V8	V9	V10	V11&12	V13	IR V14	V15	
Visit Description	~Time to Complete Measure (minutes)		Tele- assessment	Tele- assessment	Site Visit	Exp. Session 1	Int. Sessions 1.1 & 1.2	CAPS-5 T2: Tele- assessment	Int. Session 1.3	Exp. Session 2	Int. Sessions 2.1 & 2.2	Int. Session 2.3	CAPS-5 T3: Outcome: Tele- assessment	Study Termi- nation	
CAPS-5	90 (Baseline) 60 (all others)			✓				✓					√		
SDS	2			✓				✓					✓		
DSP-I	15			✓				✓					✓		
C-SSRS B	10	✓	✓		✓	√C	√		✓	√c	✓	✓		✓	
MINI	90		✓												
CIPD-SR	20	✓													
CIPD	60		✓												
LEC-5	5	✓			✓				✓			✓		√	
PCL-5	8	✓			✓				✓			✓		✓	
DDIS D	5		✓												
ACE	4				✓										
BDI-II	10 (Baseline) 5 (all others)				√									√	
CPGS	5				✓									✓	
EQ-5D-5L	3				✓									✓	
SCS	6			·	✓			·						✓	
AUDIT	3	✓												✓	
DUDIT	3	✓												✓	
SRNU	3				✓									✓	
EAT-26	6				✓									✓	
UFEC	3				✓										
SE	2					✓				✓					
~Total Time o Measures (mir		49	165	107	50	12	10	77	23	12	10	23	77	57	

<sup>A Ensure that LEC-5 and CIPD-SR results are sent to the Independent Rater

<sup>B First C-SSRS is a Lifetime assessment, other assessments are Since Last Visit
C Conducted pre- and post-IP administration, and at phone calls on Days 2 and 7 after Experimental Session

<sup>D The relevant questions (117 to 132) from the DDIS will be asked by the Independent Rater during the IR Screening visit. The entire measure will never be administered.

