#### 11.0 Concomitant Medications

## 11.1 Tapering Instructions

The site physician will record concomitant medications during Screening. If the prospective participant is being treated with psychiatric medications at enrollment, the prospective participant will be encouraged to discuss medication tapering with their outside treating physician, if any, and will be required to give the site physician permission to do so as well. The medications will then be tapered in an appropriate fashion to avoid withdrawal effects and discontinued at least five half-lives plus one additional week for stabilization before the first Experimental Session to avoid the possibility of any interaction. Additionally, participants who are taking prohibited opiates will be cross-tapered to an allowable opiate (hydrocodone, morphine, and codeine) under the care of their prescribing physician.

The site physician will consult the prescribing physician to initiate medication tapering for participants, as they must refrain from taking psychiatric medications throughout the study, with some exceptions (see Section 11.2 Allowable Concomitant Medications). The prescribing physician's opinion about medication discontinuation will documented either in writing from the prescribing physician, or in writing by the site physician documenting phone contact with the prescribing physician. Tapering will follow a time course appropriate for the medication based on its half-life, with the first Experimental Session scheduled to occur after complete washout (five half-lives plus at least 1 week for stabilization). If the health of the participant worsens after tapering, the participant will be withdrawn from the study and will be treated according to standard clinical practice. This will be recorded in the eCRF.

The therapy team will request information about any changes in medication at each contact. The site physician will be responsible for reviewing and confirming all medications collected during the study.

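### Section 6.3 promises a C-SSRS after medication washout, but none is scheduled or guaranteed for a tapered participant who completes washout and then fails before Visit 4

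*Protocol*

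**What the plan says.** **The commitment.** Protocol section 6.3, under the C-SSRS: "Participants who are discontinuing medications to participate in the study will complete the C-SSRS before and after medication washout". It is not limited to participants who go on to be dosed.

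**When the taper starts.** Table 1, Enrollment row (Visit 0): "If enrolled, begin taper, (5 half-lives plus 1 week for stabilization". This comes after the Independent Rater Screening C-SSRS.

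**What is scheduled next.** Protocol Table 7 and SAP Table 3 place the C-SSRS at site Screening, at Independent Rater Screening, and then not until Visit 4. Of these forms the table note says: "First C-SSRS is a Lifetime assessment, other assessments are Since Last Visit". At Visit 3, the first assessment after the taper, Table 1 lists "CAPS-5, SDS, and DSP-I completed by an IR via tele-assessment after taper is complete". The end-of-taper call is conditional and names no C-SSRS: "If needed, confirm medication taper and stabilization is complete and participant is eligible for Baseline CAPS-5". Section 7.2.3 lists the Visit 4 C-SSRS among the tasks for participants who are eligible at that visit.

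**What happens on failure.** Table 1, Visit 4 row: "If enrollment is not confirmed do not perform visit, complete termination". Section 4.3.3, on Pre-Dosing Early Terminations, tells the site to "notify the potential participant that they are not eligible for the study, and do not schedule additional assessments", not to perform the next visit, and to provide an Exit Plan. Section 11.1 adds a separate withdrawal route: "If the health of the participant worsens after tapering, the participant will be withdrawn from the study". It continues that such participants are treated under standard clinical practice and that this is recorded in the eCRF.

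**The concern.** Section 6.3 sets a check on both sides of washout for everyone who stops medication for the study. The schedule meets the second half of that promise only at Visit 4, and the exit rules remove Visit 4 for anyone who fails before it. A site that follows Table 1 and section 4.3.3 to the letter can therefore depart from section 6.3.

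Two things are at stake. These participants came off psychiatric medication in order to enter the trial, and serious suicidal ideation and suicidal behavior on the C-SSRS are a named safety objective (section 2.3, item 10). Also, SAP section 8.4 takes the C-SSRS baseline from Independent Rater Screening, before the taper. Scheduled C-SSRS data from after the taper therefore come only from participants who reach Visit 4.

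**Working it through.** The plan states no figure to reproduce. The check is a cross-reading of the schedule and exit rules, with two pieces of arithmetic.

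**1. Is a C-SSRS planned between the start of taper and Visit 4?**

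| Contact | C-SSRS listed? | Source |
|---|---|---|
| Independent Rater Screening (before taper) | Yes | Table 7 |
| Visit 0, taper starts | No | Tables 1, 7 |
| Visits 1 and 2 | No | Section 7.2.1, Table 7 |
| End-of-taper call, only if needed | No | Table 1 |
| Visit 3 | No | Tables 1, 7 |
| Visit 4, if performed | Yes | Table 7, section 7.2.3 |

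The column totals in Table 7 help to test the tick marks, using its minutes per measure:

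- Independent Rater Screening: C-SSRS 10 + MINI 90 + CIPD 60 + DDIS 5 = 165. The stated total is 165, so the C-SSRS is included.
- Visit 3: CAPS-5 90 + SDS 2 + DSP-I 15 = 107. The stated total is 107. With a C-SSRS it would be 117, so none is planned there.
- Visit 4: the ticked measures sum to 63 against a stated 50. The 13-minute difference cannot be assigned to one measure, so this total settles nothing. Section 7.2.3 does list the C-SSRS at Visit 4 explicitly.

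**2. Does the exit route supply one instead?**

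- Section 4.3.3 excludes additional assessments and adds an Exit Plan.
- Section 7.4.4 describes the Exit Plan as covering treatments, medications, contact details and, on request, referral. It has no suicide-risk item.
- Section 7.4.3 includes a C-SSRS in the Study Termination visit. It ties that visit to Visit 14 and extends it to participants withdrawn from treatment who stayed in follow-up. Pre-Dosing Early Terminations are not named.
- Section 4.3.4 offers Study Termination procedures to participants who drop out after dosing, if they agree. Section 4.3.3 has no matching sentence for those who leave before dosing.
- Participants who fail Enrollment Confirmation may not be re-enrolled (section 4.3.3), so no later visit fills the gap.

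**3. How long since the last scheduled form?**

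Inputs: Independent Rater Screening to Visit 0 is 2 to 14 days (section 7.1.5, Table 1). The Preparatory Period is 2 to 11 weeks from enrollment, that is 14 to 77 days (section 4.2). Visit 4 is 3 to 6 days after Visit 3 (Table 1).

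- Interval to the Visit 4 that is not performed: shortest 2 + 14 = 16 days; longest 14 + 77 = 91 days.
- Longest interval at a Visit 3 failure: 91 − 3 = 88 days.
- For a termination at the end-of-taper call, which falls within 56 days of Visit 0: at most 14 + 56 = 70 days.

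**The case against.** The strongest reply is that a missing scheduled form does not mean a missing assessment. Section 9.1.2 requires the C-SSRS per Table 7 and also as needed on clinical presentation, with an action plan for ideation scores of 4 or 5 and for suicidal behavior. Adverse events are collected from Visit 0, changes in health are asked about at Visits 1 and 2, and increases in suicidality are captured as adverse events. Participants who fail Enrollment Confirmation stay in the EDC system, and the SAP has a category for pretreatment adverse events. A reader might infer from the schedule that these participants never receive a C-SSRS, that their suicide risk goes unassessed, or that suicidality during taper is recorded only for those well enough to be confirmed. The documents do not support any of these.

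Three further limits stand:

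- The section 6.3 wording concerns the period after washout. Someone withdrawn mid-taper may not have reached that point, so it would be wrong to say that the promise is broken for every tapered participant who fails before Visit 4.
- A participant found ineligible during Visit 4 may already have completed the form.
- The Table 1 instruction to complete termination is undefined. It could be read as calling for Study Termination procedures, which include a C-SSRS, although section 4.3.3 points the other way.

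What the reply does not answer is the scheduled check itself. A form triggered by presentation depends on clinical judgment, whereas section 6.3 promises it to everyone who stops medication. The as-needed route is weakest for someone who completes washout, scores below 35 at Visit 3 and shows nothing outwardly. It is more likely to catch someone withdrawn under section 11.1 because their health worsened.

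**Conclusion.** The point holds as an inconsistency between section 6.3 and the schedule and exit rules. For a tapered participant who completes washout and fails before Visit 4, no post-washout C-SSRS is scheduled or guaranteed. The clearest case is a Visit 3 CAPS-5 below 35.

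The last scheduled form lies 16 to 91 days before the Visit 4 that is not performed, and up to about 88 days before a Visit 3 failure. These are limits of the visit windows, not expected values. They take Visit 4 as the end of a Preparatory Period counted from Visit 0, as section 4.2 does, and up to 14 of the days precede the taper. Table 1 heads the same 2 to 11 weeks as running from Visit 1, which may fall up to 12 days after Visit 0; on that reading the upper limit would be 14 + 12 + 77 = 103 days. The interval is one without a scheduled C-SSRS, not one without contact.

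The documents do not give the number of participants affected. No safety objective sets out to estimate taper risk, so this is a missed safety commitment with some loss of C-SSRS data and not a bias in a stated estimate.

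**What to change.** Reconcile section 6.3 with sections 4.3.3, 7.2.3, 7.4.3, 7.4.4, 9.1.2 and 11.1, Table 1, Table 7 and SAP Table 3, so that the schedule and exit route for tapered Pre-Dosing Early Terminations deliver the post-washout C-SSRS that section 6.3 already states. In the same amendment, define what completing termination means for this group, and state whether the section 6.3 commitment covers participants withdrawn before washout is complete. The sponsor should choose the contact at which the form is given.

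The cost is amendment wording in both documents and one form, timed at 10 minutes in Table 7, which section 6.3 allows by telephone. The end-of-taper call takes place only if needed, so it cannot be assumed to exist for every participant.

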## 6.4 Screening Measures and Reliability

## **Mini-International Neuropsychiatric Interview (MINI)**

This version of the MINI (7.0.2), a structured interview that was first developed in 1998 to be compatible with DSM and International Classification of Disease (ICD) criteria for psychiatric illnesses [77], is now compatible with DSM-5 and will be administered by a member of the Independent Rater Pool to screen for all psychiatric conditions other than personality disorders. Each module of the MINI consists of two or three questions where the answer is either "Yes" or "No," and decision-tree logic is used to determine whether to ask additional questions [78]. The MINI takes between 1-1.5 hours to perform and addresses major psychiatric disorders. MINI items were highly reliable (interrater reliability between kappa of 0.8 and 0.99, test-retest reliability between 0.6 and 0.9 for all scales save "current mania"), and diagnosis via MINI was comparable to that made with the Composite Diagnostic Interview and the SCID [78, 79] Testing on non-psychiatric samples did not create false positives [77].

#### Clinical Interview for Personality Disorders (CIPD)

A clinical interview for personality disorders (CIPD) will be conducted using either the Structured Clinical Interview for Personality Disorders DSM-5 (SCID-5-PD) or DSM-4 (SCID-4-PD) [80] or any other diagnostic measure approved by the sponsor and the responsible Ethics Committee and Competent Authority, as applicable per country.

Prior to the CIPD participants will complete a brief self-report (SR) questionnaire SCID-5-PD or SCID-4-PD or any other SR measure as applicable per country as a self-screening tool for personality disorders. Potential personality disorders that satisfy diagnostic thresholds will be

further assessed via clinical interview by a blinded IR via tele-assessment. IRs will receive training on administering these measures from a trainer. Interviews may be recorded as necessary to establish reliability of a random selection of interviews for accuracy.

#### **Life Events Checklist for DSM-5 (LEC-5)**

The LEC-5 is a 17-item self-report instrument designed to determine the presence of traumatic life events in the assessment and diagnosis of PTSD. It is a companion measure to the PCL-5 and will be used to assess PTSD. The participant indicates whether each event listed has occurred during their lifetime, permitting the possibility of marking multiple events [81].

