**Table 4: Protocol Objectives and Assessment Tools** 

Objectives	Measure	Measure Type	Administration
Eligibility	l l		1
Assess Axis 1 psychiatric disorders	MINI	Eligibility	Tele-assessment (IR)/
Assess personality disorders	CIPD	Eligibility	Tele-assessment (IR) and Self-report measure at Site
Confirm PTSD diagnosis and severity	PCL-5 with LEC-5	Eligibility	Site
Identify Dissociative Identity Disorder	DDIS	Eligibility	Site
Primary			
Assess changes in PTSD symptom severity from Visit 3 to Visit 14	CAPS-5	Outcome	Tele-assessment (IR)
Secondary			
Assess changes in clinician-rated functional impairment from Visit 3 to Visit 14	SDS	Outcome	Tele-assessment (IR)
Safety	T		
Assess incidence of positive or serious ideation and suicidal behavior	C-SSRS	Safety	Tele-assessment (IR screening) and Site
Exploratory	T		
Characterization of CAPS-5 Total Severity score at weeks 3, 8, and 14 to explore onset of treatment efficacy with a descriptive time course plot	CAPS-5	Outcome	Tele-assessment
Explore changes in PTSD symptom clusters of re-experiencing, avoidance, negative alterations in cognition and mood, sleep and hyperarousal as measured by changes in CAPS-5 subscale scores	CAPS-5 subscale scores	Outcome	Tele-assessment
Assess overall changes in clinician-rated functional impairment through item scores from Visit 3 to Visit 14	SDS item scores	Outcome	Tele-assessment
Assess changes in severity of dissociative symptoms associated with PTSD from Visit 3 to Visit 14	DSP-I	Outcome	Tele-assessment
Explore correlation of dissociative symptoms associated with PTSD with the CAPS-5 Total Severity analyses	DSP-I CAPS-5	Outcome	Tele-assessment
Explore the effect of presence of secondary traumatic stressors during the assessment period as a covariate on the CAPS-5 Total Severity analyses	LEC-5 CAPS-5	Outcome	Site and Tele-assessment
Explore the effect of adverse childhood experiences on PTSD treatment outcomes as a covariate on the CAPS-5 Total Severity analyses	ACE CAPS-5	Outcome	Site and Tele-assessment
Explore changes in PTSD symptom clusters of re-experiencing, avoidance, negative alterations in cognition and mood, and hyperarousal as measured by changes in CAPS-5 subscale scores	CAPS-5	Outcome	Tele-assessment

Objectives	Measure	Measure	Administration		
-		Type			
Assess changes in depression symptoms from Visit 4 to Visit 15	BDI-II	Outcome	Site		
Assess changes in chronic pain from Visit 4 to Visit 15	CPGS	Outcome	Site		

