## **10.2 Other Significant Events**

Significant life events that may occur during the course of the study, including death of a loved one, loss of employment, or other hardship, may have an impact on treatment outcome. The sponsor will capture these life events using the LEC-5 measure. Such events will be entered as Comments in the eCRF and if appropriate, described in the Case Study Report for data outliers, if any.

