### 13.1.1.3 Exploratory Analyses

One-group pretest-posttest Cohen's *d* effect size will be estimated. Exploratory sub-group analyses may be conducted when possible to evaluate effects and by individual demographic

characteristics (*e.g.*, age, gender, ethnicity, index trauma, ACE score, presence of secondary traumatic stressors during the assessment period with LEC-5, medication tapering, diagnosis of comorbid depression, diagnosis of comorbid diagnosis, and number of experimental sessions completed). Post-hoc exploratory analyses not described in the protocol or Statistical Analysis Plan may be performed to further examine the study data. These analyses will be clearly identified as such in the final clinical study report.

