3.4 Exploratory Objectives

These objectives may be explored to characterize participants receiving MDMA-assisted psychotherapy to support the primary objective:

- 1. Explore the effect of presence of secondary traumatic stressors (LEC-5) on the CAPS-5 Total Severity analyses
- Explore changes within-participants in PTSD symptom clusters of re-experiencing, avoidance, negative alterations in cognition and mood, and hyperarousal, as measured by changes in CAPS-5 subscale scores from Visit 3 (Baseline) to Visit 14 (13 weeks post Baseline)
- 3. Explore the effect of adverse childhood experiences (ACE) on the CAPS-5 Total Severity analyses
- 4. Explore changes in:
 - Dissociative symptoms associated with PTSD (DSP-I)
 - Depression (BDI-II)
 - Chronic pain (CPGS)
 - Quality of life (EQ-5D-5L)
 - Self-compassion (SCS)
 - Addictive behaviors including: alcohol use (AUDIT), drug use (DUDIT), and nicotine use (SRNU)
 - Eating habits (EAT-26)

- Healthcare utilization (UFEC) and economic productivity
- Subjective effects (SE)

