8.7.3 Exploratory Analyses

[figure not shown]
Post-hoc exploratory analyses not identified in this SAP may be performed to further examine the study data. These analyses will be clearly identified as such in the final clinical study report or in the clinical study report addendum.

In exploratory analyses, additional baseline covariates (age, gender, ethnicity, index trauma, complexity and severity of trauma, medication tapering, diagnosis of comorbid depression, diagnosis of comorbid Axis 2 diagnosis, adverse childhood experiences) may be assessed for inclusion in the model at a p<0.05. One-group pretest-posttest Cohen's *d* effect size will be estimated.

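### The repeated LEC-5 is described only as a lifetime checklist, so it under-records new stressors during the study for an optional exploratory analysis

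*Protocol*

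**What the plan says.** Protocol Section 6.4 holds the only description of the instrument. "The LEC-5 is a 17-item self-report instrument", and "The participant indicates whether each event listed has occurred during their lifetime". No count of occurrences, event date or shorter recall period is mentioned.

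Protocol Table 7 and SAP Table 3 schedule it at Screening, V4, V9, V13 and V15.

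Three places in the protocol give the repeats a time-bound purpose:

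- Table 4, exploratory: "Explore the effect of presence of secondary traumatic stressors during the assessment period as a covariate on the CAPS-5 Total Severity analyses".
- Section 13.1.1.3, as a possible sub-group factor: "presence of secondary traumatic stressors during the assessment period with LEC-5".
- Section 10.2, on significant life events arising during the study: "The sponsor will capture these life events using the LEC-5 measure". These events are then entered as eCRF comments.

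The SAP keeps the objective in Section 3.4 ("Explore the effect of presence of secondary traumatic stressors (LEC-5) on the CAPS-5 Total Severity analyses") but gives no rule for deriving the variable. The covariates in SAP Section 8.7.3 are "additional baseline covariates (age, gender, ethnicity, index trauma, complexity and severity of trauma, medication tapering" and further baseline items. Stressors during the study are not among them.

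**The concern.** The stated recall window is a lifetime, while the quantity wanted is what happened during the study. A lifetime yes/no item can only move from no to yes. Once a type is ticked, later events of that type leave no trace on the form. The population makes this relevant: every participant has PTSD, and the protocol does not exclude people with more than one traumatic event.

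At stake is whether exploratory objective 1 can be answered as worded, and whether the structured data can help explain an outlying V14 score, which is a purpose of Section 10.2.

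**Working it through.** The plan gives no figure to reproduce. The check is mainly a comparison of passages, followed by one illustration.

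**1. What a repeat can show.** For one event type, let the earlier and later answers be 0 (never) or 1 (ever).

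- 0 then 0: no event of that type reported.
- 0 then 1: a first-ever event, or an old event disclosed only now.
- 1 then 1: either nothing new or a further event. The two cannot be told apart.

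A new event of the same type as an index trauma ticked at Screening always falls in the third row.

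**2. What a new tick means.** Without a date, 0 then 1 cannot be placed between V3 and V14.

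- V4 falls 3 to 6 days after V3, so a type first ticked at V4 may predate baseline.
- V15 falls 1 to 9 days after V14, so a type first ticked at V15 may postdate the outcome.
- Protocol Section 1.2.3 expects the treatment to open access to information about past trauma, so a late tick may be an old event newly recalled.

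**3. Whether V4 is a usable reference.** Table 7 ticks the LEC-5 at V4, but the V4 list in Protocol Section 7.2.3 omits it. The ticked times at V4 add up to 10 + 5 + 8 + 4 + 10 + 5 + 3 + 6 + 3 + 6 + 3 = 63 minutes, against a printed total of 50. The gap of 13 equals LEC-5 (5) plus PCL-5 (8). Section 7.2.3 does list the PCL-5, so the total alone does not settle the matter. If V4 is skipped, the reference is Screening, before a Preparatory Period of 2 to 11 weeks.

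**4. Contrast with the C-SSRS.** Protocol Section 6.3 and a Table 7 footnote give the C-SSRS a lifetime form first and a since-last-visit form afterwards. The LEC-5 has no such instruction.

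**5. Other sources.** The eCRF comments are free text, and no document links them to the analysis variable. The developmental trauma record mentioned with the ACE concerns childhood and adolescence.

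**6. Illustration only.** Assume k of the 17 types are ticked at Screening and a new event is equally likely to be of any type. Share missed = k/17.

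| k | k/17 |
|---|---|
| 1 | 6% |
| 3 | 18% |
| 5 | 29% |
| 9 | 53% |

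Neither the values of k nor the even spread comes from the documents. If new events tend to repeat earlier types, the share missed is higher.

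**The case against.** The best defence is that Section 6.4 describes the LEC-5 as a screening measure, and no passage states which instruction is used at V9, V13 or V15. Sections 10.2 and 13.1.1.3 and Table 4 plainly intend an in-study window, and the form itself is not among the documents. This stands as a limit: the finding is about the plan as written. But the only window written down does not measure the stated construct, and the protocol does specify a since-last-visit form for the C-SSRS.

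The defence also holds on the following points, each of which rules out a stronger reading that might be inferred:

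- **That a planned model depends on this variable.** Only Table 4 calls it a covariate. Section 13.1.1.3 treats it as an optional sub-group factor, the objectives in both documents are optional, and SAP Section 8.7.3 omits it.
- **That repeat events are invisible to the trial.** Therapy teams ask about changes in health at every Integrative Session and phone contact, and eCRF comments may record such events. The gap is in the structured data.
- **That the estimated effect is pulled toward zero.** That would need detection to be unrelated to outcome. Here detection falls as prior trauma types rise, and the plan itself treats trauma history as possibly related to CAPS-5. Old events newly disclosed add error of the opposite kind. The direction is open.
- **That most new events are missed.** The documents give no endorsement counts, and in the illustration the share passes one half only at k = 9 or more (8/17 = 47%).

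Exclusion criterion 3 removes people judged likely to be re-exposed to significant trauma. With up to 40 participants, new events may be few. That makes them rarer, not easier to see.

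**Conclusion.** The point holds as a mismatch between instrument and construct. If the LEC-5 is repeated as Section 6.4 describes it, stressors during the study are under-ascertained, more so in participants with more prior trauma types, and newly ticked types cannot be dated. New events of a type not ticked before still show, so the variable is incomplete rather than empty.

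The consequence is confined to one optional exploratory analysis and the structured record of life events. The primary CAPS-5 estimate, the SDS analysis and the safety analyses do not use this variable. The size of the loss cannot be computed from the documents, and the k/17 figures should be read only as an illustration. The conclusion rests on the repeat forms carrying no other recall instruction or date field, since none is described. This is a minor improvement worth making.

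**What to change.** 1. Keep the lifetime form at Screening. At each repeat administration, add a since-last-visit instruction and a date for each reported event, on the same principle as the C-SSRS.
2. Define the variable in the SAP as any event dated between V3 and V14. State that it is a post-baseline exploratory factor, separate from the baseline covariates in Section 8.7.3, and whether it enters as a covariate (Protocol Table 4) or a sub-group factor (Protocol Section 13.1.1.3).
3. Reconcile Table 7 with Protocol Section 7.2.3 on whether the LEC-5 is given at V4.
4. If a share of missed events is ever quoted, label it as assumption-based.

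The cost is a small wording change to a 5-minute form in each study language, a date field, a short SAP definition and a minor protocol amendment. No visits are added.
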